An Online Self-Management Intervention for Patients with Fibromyalgia
– an RCT
Analysis Plan

Baseline Characteristics and Differences

Descriptive statistics (means and standard deviations in case of normally distributed variables or medians and interquartile ranges in case of non-normally distributed variables, and numbers and percentages in case of categorical variables) will be reported for the following baseline characteristics:

- Sociodemographic variables: age, sex, marital and relationship status, education
- Disease- and treatment related variables: medication, duration of fibromyalgia, physical and psychological comorbidities, (previously) received treatments for fibromyalgia
- Other: frequency of internet use, internet use proficiency, extraversion and neuroticism

Differences in baseline characteristics between the intervention group and control group will be examined, and between patients who completed the intervention and those who did not. For continuous outcomes, T-tests or independent samples median tests (when non-normally distributed) will be conducted. For categorical outcomes, χ^2 -tests will be conducted.

Analyses

All main analyses will be carried out following the intention-to-treat (ITT) principles. As linear mixed models are well-suited to handle missing values, missing data from drop-outs will not be imputed. Person-mean imputation will be applied when necessary to calculate scale scores. The analyses will be conducted (1) with the inclusion of covariates (primary analysis), (2) without the inclusion of covariates (sensitivity analysis) and (3) per protocol (i.e., comparing only the patients who completed the intervention with patients in the control group as a sensitivity analysis) with and without the inclusion of covariates.

Main Analyses

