To compare changes in primary and secondary outcome variables during the study period between patients in the intervention and control groups, linear mixed models will be fitted using full maximum likelihood estimation. The models will include fixed effects of time as three dummy variables: 'short-term' for baseline vs. post-intervention, 'mid-term' for baseline vs. 6-week follow-up, and 'long-term' for baseline vs. 3-month follow-up. To indicate the effect of the intervention across time, the fixed effects of interactions between group (i.e., intervention or control group) and timepoint will be included as again three dummy variables: short-term*group, mid-term*group, and long-term*group. Finally, the fixed effects of the covariates age (centered) and sex will be included. The models will include random effects of intercept and the addition of random effects of slopes will be tested with Likelihood Ratio Tests (i.e., the difference in -2LL between the alternative model and the null model using a χ^2 distribution). For each model, the variance-covariance matrix leading to the optimal model fit (i.e., the lowest Akaike's Information Criterion) will be selected using restricted maximum likelihood estimation. Values of $p < .05$ (two-tailed) will be considered as significant.

Assumptions

For each final model, the assumptions of normality, homoscedasticity and linearity will be checked by examining Q-Q plots, scatterplots of residuals versus predicted values, and scatterplots of predicted values versus observed values, respectively. In case assumptions are not met, transformations will be applied. Histograms of the residuals will be inspected for outliers. An outlier will be corrected manually if the outlier is a clear result of an error. Otherwise, the influence of an outlier will be examined by comparing results with and without the outlier. If the outlier is influential, a transformation will be applied. If not, the outlier will be retained.

Effect Sizes

Between-group effect sizes will be calculated for each outcome at post-intervention (T2), 6-week follow-up (T3), and 3-month follow-up (T4). Cohen's d effect sizes will be obtained by

performing independent T-tests in SPSS with change scores (compared to baseline) as dependent variables and group as predictor. Effect sizes of 0.2, 0.5, and 0.8 will be considered as small, medium, and large, respectively (Cohen, 1988).

Minimal Clinically Important Improvement

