The number and percentage of participants in the intervention and control group that showed minimal clinically important improvement will be calculated for the primary outcome pain coping, defined as an increase of at least 10% on the VAS pain coping scale at T2. This number is in line with previous recommendations on minimal clinically important improvement in VAS pain (Dworkin et al., 2008). Differences in minimal clinically important improvement in pain coping between the intervention and control group will be compared with the χ^2 -test.

Other Study Parameters

Cost-effectiveness

The main research question of the cost-effectiveness analyses is to investigate the cost-effectiveness of the intervention versus standard care from a societal perspective. In order to study the potential efficiency from a societal perspective, both the medical consumption (direct costs) and productivity losses (indirect costs) will be calculated. Quality-adjusted life years (QALYs) will be computed in order to perform a cost-utility analysis. Utilities (EQ-5D) will be based on the mean values for the patients at three occasions (baseline, post-treatment and three months follow-up).

Interim Analysis

Not applicable.

References

Cohen J. *Statistical power analysis for the behavioral sciences*. Hillsdale, N.J.: L. Erlbaum Associates, 1988.

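### The T2 responder test is an unadjusted chi-square that makes no use of baseline coping; it loses some precision and is open to bias if dropout relates to baseline differently in the two arms

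*SAP*

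**What the plan says.** Under *Minimal Clinically Important Improvement* the SAP dichotomises the primary outcome, pain coping. Response is "defined as an increase of at least 10% on the VAS pain coping scale at T2". The SAP then says that "The number and percentage of participants in the intervention and control group that showed minimal clinically important improvement will be calculated", and that "Differences in minimal clinically important improvement in pain coping between the intervention and control group will be compared with the" χ²-test. It names no covariate, effect estimate, interval, denominator or rule for patients without a T2 value.

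Two other sections bear on this:

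- *Analyses* explains the handling of dropouts: "As linear mixed models are well-suited to handle missing values, missing data from drop-outs will not be imputed".
- *Main Analyses* describes the mixed models. There "the fixed effects of interactions between group (i.e., intervention or control group) and timepoint will be included", with time dummies and no separate group term listed, so baseline means are in effect held equal between the arms. In addition, "the fixed effects of the covariates age (centered) and sex will be included".

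Nothing in the SAP adjusts the responder comparison for baseline coping.

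**The concern.** A patient who starts low on coping has more room to rise, and tends to rise through regression to the mean; a patient who starts high tends to fall. Baseline is therefore a strong predictor of response. The chi-square uses it only to classify each patient and then ignores it. Two things follow.

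- **Precision.** Chance imbalance in baseline coping feeds directly into the responder difference.
- **Missing T2 values.** The reason given for not imputing is a property of mixed models, which a chi-square does not share. If patients without T2 are simply left out, the result depends on who left. Where dropout relates to baseline coping differently in the two arms, the arms compared no longer have the same baseline distribution.

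The mixed model carries the main T2 inference, so that conclusion is not at stake. But this is the SAP's only between-arm test of clinically important improvement on the primary outcome.

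**Working it through.** The SAP states no sample size, SD, correlation, responder rate or dropout rate, so there is no figure of its own to reproduce. All inputs below are assumptions, varied over a range. Unless stated otherwise, response is read as a rise of 10 points on a 0–100 scale.

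**Step 1. Dependence on baseline, no treatment effect.** Assume mean 40 and SD 20 at both visits, with correlation ρ. Given baseline b, T2 is normal with mean 40 + ρ(b − 40) and SD 20√(1 − ρ²). With whole-number scores, a 10-point rise means at least 9.5 before rounding:

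P(response | b) = Φ{[40 + ρ(b − 40) − b − 9.5] / [20√(1 − ρ²)]}

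For ρ = 0.6 the residual SD is 16:

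- b = 20: Φ[(28 − 20 − 9.5)/16] = Φ(−0.094) = 46%
- b = 60: Φ[(52 − 60 − 9.5)/16] = Φ(−1.094) = 14%

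The same formula gives 55% vs 12% at ρ = 0.4 and 32% vs 13% at ρ = 0.8.

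**Step 2. The reading of 10%.** Now assume mean 50, SD 20, a general shift of +2 and ρ = 0.5. At baselines 30, 50 and 70, response is 55%, 32% and 15% if 10% means scale points. It is 70%, 43% and 19% if it means 10% of the patient's own baseline. Both readings depend on baseline, and the two definitions give clearly different responder rates.

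**Step 3. Chance imbalance.** With no treatment effect, a baseline difference of 0.2 SD between arms moves the unadjusted responder difference by 2.7 to 4.5 points, and 0.3 SD moves it by 4.1 to 6.7 points (correlation 0.7 down to 0.3).

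**Step 4. Precision.** Simulated trials, 100 per arm, 20% random dropout in each arm. Power is for a 0.5 SD effect, chi-square against a logistic model standardised to all randomised patients:

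| Correlation | Fall in SD of risk difference | Power, chi-square to adjusted |
|---|---|---|
| 0.4 | 8 to 9% | 63% to 72–74% |
| 0.6 | 3 to 6% | 81% to 86% |
| 0.8 | 1 to 3% | 97–98% to 98–98.5% |

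Without dropout, for totals of 100 to 250 and correlations of 0.3 to 0.85, the adjusted variance is 0.72 to 0.96 of the unadjusted. Since 1/0.96 = 1.04 and 1/0.72 = 1.39, this equals 4% to 39% more patients. With no effect and low-baseline patients dropping out there is no clear gain (SD 7.1 points unadjusted vs 7.2 adjusted at correlation 0.6).

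**Step 5. Bias when only patients with T2 are compared.** Correlation 0.6, 100 per arm, dropout odds ratio 2 or 2.7 per SD of baseline:

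| Dropout | Complete-case bias, points | Adjusted |
|---|---|---|
| Random | about 0.1 or less | about 0.1 or less |
| 30% vs 10%, related to baseline | 1.7 to 3.3 | within 0.2 |
| 20% each, related in one arm only | 1.8 to 3.2 | within 0.2 |
| 20% each, opposite directions | 3.7 to 5.5 | within 0.2 |

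In the three baseline-related rows, type I error is 5.5% to 11.8% for the chi-square (mostly under 8%) and 4.8% to 6.6% adjusted. Over correlations 0.4 to 0.8 and 40 to 100 per arm, complete-case bias is about 2 to 8 points and adjusted bias at most about 0.3.

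A second set of assumptions agrees (150 patients in total, correlation 0.5, about 25% dropout, related to baseline in the intervention arm only). The observed difference is 10.7 points against a true 15.6 when low-baseline patients leave, and 20.1 against 15.2 when high-baseline patients leave. The standardised estimates are 15.6 and 15.3.

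**Step 6. What adjustment does not repair.** If dropout depends on the unseen T2 value, bias is 5.1 to 7.2 points complete-case and still 3.9 to 6.0 adjusted. If it depends on coping at T3 and T4, bias is 2.7 to 3.4 and 1.7 to 2.0.

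**Step 7. Small samples.** At 40 per arm with no dropout or random dropout, a test based on the standardised risk difference and its delta-method standard error rejects in 6.1% to 7.2% of null trials, against 4.7% to 5.2% for the chi-square. Taking the p-value from the logistic arm coefficient brings this to about 4% to 6%.

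**The case against.** The strongest reply is that the planned test is not wrong. Randomisation makes regression to the mean act equally in both arms. With complete data, type I error is 4.9% to 5.4% at 150 patients. Baseline already enters through the definition of response, and the analysis is supplementary. All of this stands.

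Three stronger readings are tempting, and the SAP does not support them.

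- A reader might infer that the chi-square contradicts the SAP's rule making the analysis with covariates primary. That rule sits with the mixed models, and its only named covariates are age and sex. It neither clearly governs the responder test nor calls for adjustment by baseline coping. The case for adjustment rests on statistical grounds.
- A reader might infer that the SAP prescribes a complete-case comparison. It does not state the denominator; counting patients without T2 as non-responders fits the text equally well. The choice matters. With a true rate of 40% in both arms, 30% vs 10% missing and dropouts responding at 20%, completers give (0.40 − 0.06)/0.70 − (0.40 − 0.02)/0.90 = +6.3 points, while non-responder counting gives 0.34 − 0.38 = −4.0. This swing comes from the denominator and the assumed dropouts, not from lack of adjustment.
- A reader might infer that adjustment settles the missing-data question. It removes only the part that works through observed baseline (Step 6).

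It is also fair to say that the dropout patterns with sizeable bias were chosen, and that the precision gain is slight at high correlation.

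**Conclusion.** The point holds in a limited form. The unadjusted chi-square is a valid but less efficient test, and it is unprotected if T2 is missing in a way that relates to baseline coping differently by arm. The SAP's stated reason for not imputing does not cover it. The precision loss is clear at correlations of 0.4 to 0.6 and slight at 0.8. The possible bias is several points under baseline-related dropout and essentially nil under random dropout.

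Which case applies cannot be told from the SAP, so these figures show what could happen rather than forecast it. The main mixed-model result is unaffected. The change is still worth making, because the covariate is already needed to define response.

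**What to change.** Under *Minimal Clinically Important Improvement*:

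1. Make the main responder comparison a logistic regression on arm, baseline coping, age and sex in patients with T2. Take the p-value from the arm coefficient (Wald or likelihood-ratio).
2. Report a risk difference standardised to all randomised patients with a 95% CI, by bootstrap or with a small-sample correction if the arms are small.
3. Keep the chi-square as a sensitivity analysis, state its denominator, and report the number without T2 in each arm.
4. State whether 10% means scale points or a share of the patient's own baseline.

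Multiple imputation of T2 coping by arm, using T3 and T4 where they exist, is an optional addition.

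The cost is a few sentences and one regression, with no new data. The downsides are slightly more analysis work, reliance on a model, a slightly liberal delta-method interval at about 40 per arm, and only partial removal of bias if missingness depends on the unseen T2 value.

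### The QALY rule uses EQ-5D values that include baseline but states no adjustment for baseline utility, so chance imbalance stays in the incremental QALY and precision is lost; time weighting is also unstated

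*SAP*

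**What the plan says.** The cost-effectiveness paragraph sets out to "investigate the cost-effectiveness of the intervention versus standard care from a societal perspective". It states that "Quality-adjusted life years (QALYs) will be computed in order to perform a cost-utility analysis", and its one rule for the utilities is "Utilities (EQ-5D) will be based on the mean values for the patients at three occasions (baseline, post-treatment and three months follow-up"). No estimation model, covariate or time weighting follows.

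The only covariates named in the SAP are in Main Analyses, where "the fixed effects of the covariates age (centered) and sex will be included". Those models are introduced with a limited scope: "To compare changes in primary and secondary outcome variables during the study period between patients in the intervention and control groups, linear mixed models". Cost-effectiveness stands apart, under Other Study Parameters.

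On missing data, the Analyses section says "As linear mixed models are well-suited to handle missing values, missing data from drop-outs will not be imputed". The assessments after baseline are "post-intervention (T2), 6-week follow-up (T3), and 3-month follow-up (T4"); the EQ-5D rule omits the 6-week one. The SAP does not give the length of the intervention.

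**The concern.** Baseline utility belongs in an area under the curve, so including it is not the fault. The gap is that it enters the result unadjusted. Baseline EQ-5D contributes directly through its own weight, and indirectly because later values correlate with it. If one arm starts higher by chance, its QALY total is higher without any treatment effect. The noise that baseline could explain also stays in the comparison.

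Extending the covariates of Main Analyses to the QALY would not cure this, because they are age and sex only.

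The incremental QALY is the denominator of the cost-utility ratio, so an imprecise or shifted value makes the ratio unstable. Because the time weighting is not stated, two analysts could also obtain different QALYs from the same data.

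**Working it through.** The SAP states no QALY figure, so there is nothing to reproduce. The check compares the unadjusted area with a baseline-adjusted one.

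**Inputs from the SAP.** Three EQ-5D occasions: baseline, post-treatment and three-month follow-up.

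**Assumptions, not in the SAP.** Equal SDs (set to 1); a common correlation ρ of 0.4 to 0.7 between occasions. Let t1 be the time from baseline to post-treatment, t2 the time from there to follow-up, and T = t1 + t2. There are two timelines:
- A: three months counted from post-treatment, so t2 = 13 weeks, with t1 = 6, 8 or 13.
- B: three months counted from baseline, so T = 13 weeks, with t1 = 6 or 8.

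**Formulas.**
- Trapezoid weights: w0 = t1/(2T), w1 = 1/2, w2 = t2/(2T).
- Share of a baseline imbalance carried into the area: c = w0 + (1 − w0)ρ.
- Unadjusted variance: V = w0² + w1² + w2² + 2ρ(w0w1 + w0w2 + w1w2).
- Variance after adjustment for baseline: V − c².
- SE ratio, unadjusted to adjusted: √[V/(V − c²)].

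**Worked case: timeline A, t1 = 8, ρ = 0.6.** The weights are 8/42 = 0.190, 0.5 and 13/42 = 0.310. Then c = 0.190 + 0.810 × 0.6 = 0.676, V = 0.753 and V − c² = 0.753 − 0.457 = 0.296. The SE ratio is √(0.753/0.296) = 1.60.

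**Range.**

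| Timeline | t1 (weeks) | w0 | c, ρ = 0.4 to 0.7 | SE ratio, ρ = 0.4 to 0.7 |
|---|---|---|---|---|
| A | 6 | 0.158 | 0.49 to 0.75 | 1.28 to 1.78 |
| A | 8 | 0.190 | 0.51 to 0.76 | 1.31 to 1.84 |
| A | 13 | 0.250 | 0.55 to 0.78 | 1.39 to 1.96 |
| B | 6 | 0.231 | 0.54 to 0.77 | 1.37 to 1.92 |
| B | 8 | 0.308 | 0.58 to 0.79 | 1.48 to 2.09 |

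Under timeline A, if adjacent occasions correlate at 0.5 to 0.7 and the first and last at 0.2 less, the SE ratio is 1.28 to 1.73. The result does not hinge on a common correlation.

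**In QALY units.** Take an assumed baseline imbalance of 0.05, ρ = 0.5, t1 = 8 and timeline A. Then c = 0.190 + 0.810 × 0.5 = 0.595, and 0.05 × 0.595 × 21/52 = 0.012 QALY appears with no treatment effect.

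**Equal-average reading only.** If each patient's three values are averaged with weights of 1/3, the ratio of the measured gain to the area-based gain is (1/3)(d1 + d2) / (d1/2 + d2·t2/(2T)). Here d1 and d2 are the effects at post-treatment and follow-up.
- Sustained effect (d1 = d2): 79%, 82% and 89% under A (6, 8, 13 weeks); 87% and 96% under B (6, 8 weeks).
- Effect at follow-up only (d1 = 0): 97%, 108% and 133% under A; 124% and 173% under B.

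The error can therefore go either way. Baseline weighs 1/3 under this reading, so 60 to 80% of an imbalance is carried and the SE ratio is 1.58 to 2.24.

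**The case against.** The strongest reply is that the paragraph is a short summary of inputs for a non-primary analysis, that silence is not a decision against adjustment, and that a protocol not shown here may settle the matter. Part of this stands: the point carries modest weight, and a fuller economic plan could answer it. But how an incremental QALY is formed and estimated is ordinary SAP content. This SAP does state a rule, and followed as written that rule leaves baseline utility unadjusted.

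Three stronger readings are tempting, and the SAP does not support them.

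- A reader might infer that the QALY comparison is biased. With complete data it is not: under randomisation the unadjusted difference is right on average. The loss is in precision and in the error given the imbalance that occurs.
- A reader might infer that the plan fixes a wrong weighting. The sentence can equally mean group means at each occasion, from which a correct area can be formed. The weighting error exists only under the equal-average reading.
- A reader might infer that drop-out will bias the QALY by some percentage. The SAP's reason for not imputing is the mixed model, and the cost-effectiveness paragraph does not place the QALY in one, so that reason does not reach it. But the SAP does not say that the no-imputation rule covers the QALY, and it gives no drop-out rate or mechanism. If the rule does apply, means of available patients would come from different patients at each occasion. No size can be put on this.

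**Conclusion.** The point holds as a fault of efficiency and specification, of minor to moderate severity, confined to the cost-utility analysis. The precision loss and the carried imbalance arise under either reading of the sentence. In the worked case the unadjusted variance is 0.753/0.296 = 2.5 times the adjusted one, a large loss when the baseline values are collected anyway.

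The direction is firm: at any positive correlation, adjustment for baseline reduces the variance in this setting. The size is less certain, because intervention length, correlations and the origin of the three-month count are all assumed. The departure from the area under the curve is conditional on the equal-average reading, and drop-out is a secondary, conditional remark.

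**What to change.** State that QALYs are the trapezoidal area under the EQ-5D utility curve over the three assessment times, and that the incremental QALY is adjusted for baseline utility, by one of two routes.

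(a) Fit the linear mixed model of Main Analyses to EQ-5D utility, with short-term and long-term dummies, their interactions with group, age and sex. Main Analyses lists time effects and says that "the fixed effects of interactions between group (i.e., intervention or control group) and timepoint will be included as again three dummy variables", with no group main effect; keeping that form holds the baseline means equal. Then

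incremental QALY = (short-term × group effect) × (t1 + t2)/2 + (long-term × group effect) × t2/2,

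with t1 and t2 in years. Utility must stay untransformed. The Assumptions section calls for transformation when model assumptions fail or an outlier is influential, and on a transformed scale a coefficient times years is not a QALY. The text should therefore exempt this model explicitly. Uncertainty in the cost-utility ratio comes from resampling patients and refitting.

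(b) Compute per-patient areas and regress them on group with baseline utility, age and sex, using multiple imputation. The text should name this as an exception to the no-imputation rule in the Analyses section.

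The cost is a few sentences, a little extra analysis work and one stated exception: to the transformation rules under (a), or to the no-imputation rule under (b). No new data are needed.
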